Appendix B Eastern Cooperative Oncology Group Performance Status scale

ECOG Performance Status Scale

ECOG PS	0	Normal, fully functional
ECOG PS	1	Fatigue without significant decrease in daily activity
ECOG PS	2	Fatigue with significant impairment of daily activities or bed rest <50% of waking hours
ECOG PS	3	Bed rest/sitting >50% of waking hours
ECOG PS	4	Bedridden or unable to care for self

Appendix C Guidance on contraceptive methods and collection of pregnancy information

DEFINITIONS

Nonreproductive potential

1. Premenopausal female with 1 of the following:
 - Documented hysterectomy,
 - Documented bilateral salpingectomy,
 - Documented bilateral oophorectomy.
2. Postmenopausal
 - A postmenopausal state is defined as no menses for 12 months without an alternative medical cause. A high follicle stimulating hormone (FSH) level in the postmenopausal range may be used to confirm a postmenopausal state in women not using hormonal contraception or hormonal replacement therapy (HRT). However, in the absence of 12 months of amenorrhea, a single FSH measurement is insufficient.
 - Females on hormone replacement therapy (HRT) and whose menopausal status is in doubt will be required to use 1 of the highly effective contraception methods if they wish to continue their HRT during the study. Otherwise, they must discontinue HRT to allow confirmation of postmenopausal status before study enrolment.

Reproductive potential (WOCBP)

A woman is considered of reproductive potential (WOCBP), ie, fertile, following menarche and until becoming postmenopausal unless permanently sterile. Permanent sterilization methods include hysterectomy, bilateral salpingectomy and bilateral oophorectomy.

CONTRACEPTIVE GUIDANCE

Male subjects

- Male subjects with heterosexual partners of reproductive potential (WOCBP) are eligible to participate if they agree to use the following during the protocol defined timeline:
 - Refrain from donating sperm,

and

 - At least 1 of the following conditions applies:
 - Are and agree to remain abstinent from penile-vaginal intercourse on a long term and persistent basis, when this is their preferred and usual lifestyle.

or

 - Agree to use a male condom plus an additional contraceptive method with a failure rate of <1% per year (see table for female subjects).
- Men with a pregnant or breastfeeding partner must agree to remain abstinent from penile-vaginal intercourse or use a male condom for the time defined in the protocol

Highly Effective Contraceptive Methods That Are User Dependent Failure rate of <1% per year when used consistently and correctly^a

• Combined (estrogen- and progestogen-containing) hormonal contraception associated with inhibition of ovulation^b
– Oral,– Intravaginal,– Transdermal.

• Progestogen-only hormone contraception associated with inhibition of ovulation^b
– Oral,– Injectable.
Highly Effective Methods That Are User Independent

• Implantable progestogen-only hormone contraception associated with inhibition of ovulation^b.

• Intrauterine device (IUD).

• Intrauterine hormone-releasing system (IUS).

• Bilateral tubal occlusion.

• Vasectomized partner. (Vasectomized partner is a highly effective contraceptive method provided that the partner is the sole sexual partner of the woman of childbearing potential and the absence of sperm has been confirmed. If not, an additional highly effective method(s) of contraception should be used. Spermatogenesis cycle is approximately 90 days.)

• Sexual abstinence. (Sexual abstinence is considered a highly effective method only if defined as refraining from heterosexual intercourse during the entire period of risk associated with the study drug. The reliability of sexual abstinence needs to be evaluated in relation to the duration of the study and the preferred and usual lifestyle of the subject.)
NOTES: 
a) Typical use failure rates may differ from those when used consistently and correctly. Use should be consistent with local regulations regarding the use of contraceptive methods for subjects participating in clinical studies.
 
b) Hormonal contraception may be susceptible to interaction with the study drug, which may reduce the efficacy of the contraceptive method. In this case TWO highly effective methods of contraception should be used during the treatment period and for at least 6 months [corresponding to time needed to eliminate study treatment plus 30 days for study treatments with genotoxic potential] after the last dose of study treatment.

Female subjects:

Highly Effective Contraceptive Methods That Are User Dependent
Failure rate of <1% per year when used consistently and correctly^a

• Combined (estrogen- and progestogen-containing) hormonal contraception associated with inhibition of ovulation^b
– Oral,– Intravaginal,– Transdermal.

• Progestogen-only hormone contraception associated with inhibition of ovulation^b
– Oral,– Injectable.
Highly Effective Methods That Are User Independent

• Implantable progestogen-only hormone contraception associated with inhibition of ovulation^b.

• Intrauterine device (IUD).

• Intrauterine hormone-releasing system (IUS).

• Bilateral tubal occlusion.

• Vasectomized partner. (Vasectomized partner is a highly effective contraceptive method provided that the partner is the sole sexual partner of the woman of childbearing potential and the absence of sperm has been confirmed. If not, an additional highly effective method(s) of contraception should be used. Spermatogenesis cycle is approximately 90 days.)

• Sexual abstinence. (Sexual abstinence is considered a highly effective method only if defined as refraining from heterosexual intercourse during the entire period of risk associated with the study drug. The reliability of sexual abstinence needs to be evaluated in relation to the duration of the study and the preferred and usual lifestyle of the subject.)
NOTES: a) Typical use failure rates may differ from those when used consistently and correctly. Use should be consistent with local regulations regarding the use of contraceptive methods for subjects participating in clinical studies. b) Hormonal contraception may be susceptible to interaction with the study drug, which may reduce the efficacy of the contraceptive method. In this case TWO highly effective methods of contraception should be used during the treatment period and for at least 6 months [corresponding to time needed to eliminate study treatment plus 30 days for study treatments with genotoxic potential] after the last dose of study treatment.

COLLECTION OF PREGNANCY INFORMATION

Male subjects with partners of reproductive potential who become pregnant

- The Investigator will attempt to collect pregnancy information on any female partner of a male study subject who becomes pregnant while participating in this study. This applies only to subjects who receive study treatment.
- After obtaining the necessary signed informed consent from the pregnant female partner directly, the Investigator will record pregnancy information on the appropriate form and submit it to the Sponsor within 24 hours of learning of the partner's pregnancy.
- Partner will also be followed to determine the outcome of the pregnancy. Information on the status of the mother and child will be forwarded to the Sponsor.
- Generally, follow-up will be no longer than 6 to 8 weeks following the estimated delivery date. Any termination of the pregnancy will be reported regardless of fetal status (presence or absence of anomalies) or indication for procedure.

Female subjects who become pregnant

- The Investigator will collect pregnancy information on any female subject, who becomes pregnant while participating in this study.
- Information will be recorded on the appropriate form and submitted to the Sponsor within 24 hours of learning of a participant's pregnancy.
- Participant will be followed to determine the outcome of the pregnancy. The Investigator will collect follow-up information on participant and neonate, which will be forwarded to the Sponsor. Generally, follow-up will not be required for longer than 6 to 8 weeks beyond the estimated delivery date.
- Any termination of pregnancy will be reported, regardless of fetal status (presence or absence of anomalies) or indication for procedure.
- While pregnancy itself is not considered to be an AE or SAE, any pregnancy complication or elective termination of a pregnancy will be reported as an AE or SAE.
- A spontaneous abortion is always considered to be an SAE and will be reported as such.

Any SAE occurring as a result of a post-study pregnancy which is considered reasonably related to the study treatment by the Investigator, will be reported to the Sponsor as described in [Section 10.4.3](#). While the Investigator is not obligated to actively seek this information in former study subjects, he or she may learn of an SAE through spontaneous reporting.

Appendix D National Cancer Institute Common Terminology Criteria for Adverse Events

Refer to NCI CTCAE v4.03 in the Study Reference Manual, or online at the following NCI website:

<http://ctep.cancer.gov/reporting/ctc.html>

1. Toxicity grade should reflect the most severe degree occurring during the evaluated period, not an average.
2. When 2 criteria are available for similar toxicities, the one resulting in the more severe grade should be used.
3. The evaluator must attempt to discriminate between disease/treatment and related signs/symptoms.
4. An accurate baseline prior to therapy is essential.

Appendix E Calculation of Cockcroft and Gault formula

$$\text{Creatinine clearance} = \frac{(140 - \text{age [years]} \times \text{body mass [kg]})}{\text{Plasma creatinine (mg/dL)} \times 72} \times \text{Gender correction factor (male: 1.00; female: 0.85)}$$

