--	--

	
E 06. Adverse events (AEs) (excluding alopecia and those listed in the specific exclusion criteria) from any prior anticancer therapy of Grade >1 (National Cancer Institute Common Terminology Criteria for Adverse Events [NCI CTCAE] v4.03; see Appendix D) at the time of randomization.
 
E 07. Wash out period of less than 3 weeks or 5 half-lives from previous antitumor chemotherapy, immunotherapy, or any investigational treatment.
 
E 08. Patient has received wide field radiotherapy ≤ 4 weeks prior to starting study treatment, or limited field radiation for palliation ≤ 2 weeks prior to starting study treatment, or has not recovered from the side effects of such therapy.
 
E 09. Patient has undergone major surgery ≤ 3 weeks prior to starting study treatment, or has not recovered from the side effects of major surgery.
 
E 10. History of brain metastasis (other than totally resected or previously irradiated and nonprogressive/relapsed), spinal cord compression or carcinomatous meningitis, or new evidence of brain leptomeningeal disease.
 
E 11. Prior malignancy. Adequately treated basal cell or squamous cell skin or superficial (pTis, pTa, and pT1) and bladder cancer are allowed, as well as any other cancer for which treatment has been completed ≥ 3 years ago and from which the patient has been disease-free for ≥ 3 years.
 
E 12. Participation in another clinical trial and any concurrent treatment with any investigational drug within 30 days prior to randomization.
 
E 13. Prior treatment with eribulin as last therapy prior to enrollment, or prior maytansinoid treatments (DM1 or DM4 antibody-drug conjugates [ADCs]).
 
Related to study treatment
 
E 14. Acquired immunodeficiency syndrome (AIDS-related illnesses) or known HIV disease requiring antiretroviral treatment.
 
E 15. Known active hepatitis A, B, or C infection that requires treatment.
 
E 16. Known intolerance to infused protein products including other monoclonal antibodies and ADCs.
 
E 17. Poor bone marrow reserve as defined by absolute neutrophil count $< 1.5 \times 10^9/L$ or platelets $< 100 \times 10^9/L$ or hemoglobin < 9 g/dL.
 
E 18. Poor organ function as defined by 1 of the following:
 
a) Total bilirubin > 1.5 x upper limit of normal (ULN) (except patients with Gilbert's syndrome: total bilirubin ≤ 3.0 x ULN, with direct bilirubin ≤ 1.5 x ULN),b) Aspartate aminotransferase, alanine aminotransferase, or alkaline phosphatase > 2.5 x ULN; except > 5 x ULN in case of documented liver metastasis or alkaline phosphatase > 5 x ULN in case of documented bone metastasis,c) Serum creatinine > 1.5 x ULN, except if calculated creatinine clearance ≥ 60 mL/min (as per Cockcroft-Gault formula, see Appendix E). 
E 19. Symptomatic peripheral neuropathy Grade ≥ 2 (NCI CTCAE v4.03).

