7.2.2 Exclusion criteria related to the current knowledge of Sanofi compound

- E 14. Acquired immunodeficiency syndrome (AIDS-related illnesses) or known HIV disease requiring antiretroviral treatment.
- E 15. Known active hepatitis A, B, or C infection that requires treatment.
- E 16. Known intolerance to infused protein products including other monoclonal antibodies and ADCs.
- E 17. Poor bone marrow reserve as defined by absolute neutrophil count (ANC) $<1.5 \times 10^9/L$ or platelets $<100 \times 10^9/L$ or hemoglobin $<9 \text{ g/dL}$.
- E 18. Poor organ function as defined by 1 of the following:
 - a) Total bilirubin $>1.5 \times$ upper limit of normal (ULN) (except patients with Gilbert's syndrome: total bilirubin $\leq 3.0 \times$ ULN, with direct bilirubin $\leq 1.5 \times$ ULN),
 - b) Aspartate aminotransferase (AST), alanine aminotransferase (ALT), or alkaline phosphatase $>2.5 \times$ ULN; except $>5 \times$ ULN in case of documented liver metastasis or alkaline phosphatase $>5 \times$ ULN in case of documented bone metastasis,
 - c) Serum creatinine $>1.5 \times$ ULN, except if calculated creatinine clearance $\geq 60 \text{ mL/min}$ (as per Cockcroft-Gault formula; see [Appendix E](#)).
- E 19. Symptomatic peripheral neuropathy Grade ≥ 2 (NCI CTCAE v.4.03).
- E 20. Previous history of chronic corneal diseases (even if asymptomatic) or unresolved acute nonrecurrent corneal conditions.
- E 21. Patients wearing contact lenses who are not willing to stop wearing them for the duration of the study.
- E 22. Medical conditions requiring concomitant administration of strong CYP3A4 inhibitors, unless it can be discontinued at least 2 weeks before 1st administration of SAR566658 (see [Appendix F](#)).
- E 23. Contraindications to the use of ophthalmic vasoconstrictor and/or corticosteroid as per package insert of each drug, including the following: increased intraocular pressure, prior or current glaucoma, narrow-angle glaucoma, ongoing eye infection, uncontrolled hypertension, known/suspected allergy to constituents of the preparation (such as sodium bisulfite).

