8.2.3.2 Treatment delay

At Day 22, a treatment delay ≥ 4 days should be justified (ie, to be reported in the eCRF). Study treatment may be delayed up to 2 weeks to allow recovery from acute toxicity. In case of a delay due to IMP-related AEs ≥ 2 weeks (except for alopecia), the patient will be withdrawn from the treatment.

The dose of SAR566658 will be modified in case of AEs. Dose modifications are summarized in [Table 3](#).

Table 3 - Dose modifications for SAR566658

Adverse event	Grade 2	Grade 3	Grade 4
Diarrhea	Delay ^a next infusion until recovery (Grade ≤1). No dose reduction required.	On Day 8, omit the dose. On Day 22, delay ^a next infusion until recovery (Grade ≤1): - 1st episode: reduce dose by 1 dose level, - 2nd episode: reduce dose by 1 more dose level, - 3rd episode: withdraw from study treatment.	
Creatinine increase	No delay, in case of creatinine >1.5 x ULN to calculate creatinine clearance (CLCr) ^b on D21: - If ≥50 mL/min, no dose modification, - If clearance ≥30 mL/min and < 50 mL/min, reduce dose by 1 dose level, - If clearance <30 mL/min, withdraw from study treatment.		
Peripheral neuropathy	No delay. Reduce by 1 dose level.	Delay ^a next infusion until recovery (Grade ≤1): - 1st episode: reduce dose by 1 dose level, - 2nd episode: reduce dose by 1 more dose level, - 3rd episode: withdraw from study treatment.	Withdraw from study treatment.
Total bilirubin elevation	In case of bilirubin >1.5 x ULN: On Day 8, omit the dose. On Day 22, delay ^a until recovery to bilirubin ≤1.5 x ULN and then reduce by 1 dose level. If no recovery after 2 dose reductions, withdraw from study treatment.		
Transaminases elevation	On Day 8, omit the dose. On Day 22, delay ^a until recovery to AST/ALT Grade ≤1. No dose adjustment.	On Day 8, omit the dose. On Day 22, delay ^a until recovery to AST/ALT Grade ≤1: - 1st episode: reduce dose by 1 dose level, - 2nd episode: reduce dose by 1 more dose level, - 3rd episode: withdraw from study treatment.	Withdraw from study treatment.

Dose reduction levels provided in [Table 2](#).

^a A maximum of 2 weeks delay at D22, otherwise the patient will be withdrawn from study treatment.

^b As per Cockcroft-Gault formula; see [Appendix E](#).

Abbreviations: ALT: Alanine aminotransferase; AST: Aspartate aminotransferase; D: day; ULN: upper limit of normal.

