- **Blood chemistry and coagulation tests** within 7 days prior Day 1 Cycle 1 (time between blood chemistry and coagulation work-up and Day 1 Cycle 1 should not exceed 7 days; if time exceeds 7 days, blood chemistry and coagulation work-up should be repeated to check that eligibility criteria are still met). Electrolytes: sodium, potassium, calcium, phosphate, and chloride. Renal function: creatinine, creatinine clearance if creatinine >1.5 x ULN, BUN or urea. Liver function: AST, ALT, total bilirubin, conjugated bilirubin, and alkaline phosphatase. Others: glucose, lactate dehydrogenase (LDH), albumin, and total protein. Coagulation test: International Normalized Ratio (INR).
- **Serum pregnancy test** for women of child-bearing potential within 7 days prior the first study treatment administration.
- **Tumor assessment** within 21 days prior to first study treatment administration: (abdominal/chest) CT scan or MRI, and all other examinations as clinically indicated (eg, brain CT scan or MRI in case of clinical suspicion of central nervous system involvement) to assess all TARGET or NON TARGET lesions (measurable and nonmeasurable). CT scan/MRI will be preferred to X-ray for the purposes of efficacy assessment. To ensure comparability, the imaging should be performed using identical techniques throughout the study period (ie, CT scan or MRI, scans performed immediately following bolus contrast administration using a standard volume of contrast, the identical contrast agent, and preferably the same scanner). When available, spiral CT acquisition should be done. Slice thickness should be adapted to the anatomical area and presumed size of the lesions. Slice thickness of 5 to 8 mm should be favored rather than 10 mm, especially during spiral acquisition.

If limitations appear in volume acquisition, it is encouraged to choose a 1.5 pitch and thin slices, rather than a 1 pitch with thick slices. A centimeter scale should appear on films.

- **Other investigations** if clinically indicated.

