2.1.4.4 Laboratory safety variables

Laboratory data consists of blood analysis, including hematology and biochemistry.

Blood samples for clinical laboratories will be taken at Day 8, Day 15 and Day 21 during the first two cycles (except for INR only at Day 21) and then at Day 8 and Day 21 for hematology and Day 21 for clinical chemistry and INR at subsequent cycles and then at end of treatment. The laboratory parameters will be classified as follows:

- Hematology:
 - **Red blood cells (RBC) and platelets and coagulation:** hemoglobin, platelet count, international normalized ratio (INR).
 - **White blood cells (WBC):** WBC with differential (neutrophils, lymphocytes, monocytes, basophils, eosinophils), absolute neutrophil count (ANC).

- Clinical chemistry:
 - **Metabolism:** blood glucose, lactate Dehydrogenase (LDH), total protein, albumin,
 - **Electrolytes:** sodium, potassium, chloride, calcium, corrected serum calcium (calculated according to Corrected calcium formula, see [Section 2.5.1](#)), phosphate,
 - **Renal function:** serum creatinine, creatinine clearance (calculated according to both Cockcroft-Gault formula, see [Section 2.5.1](#)), urea or blood urea nitrogen (BUN),
 - **Liver function:** alanine aminotransferase (ALT), aspartate aminotransferase (AST), alkaline phosphatase, total and direct bilirubin.

Moreover, serum pregnancy test will be performed at baseline, during on-treatment period and end of treatment period for women of child bearing potential.

Laboratory values will be analyzed after conversion into standard international units by data management. These converted values will be graded according to the NCI-CTCAE version 4.03 whenever applicable, using laboratory normal ranges (liver function tests, creatinine, creatinine clearance, LDH) provided by the laboratory analyzing the sample whenever possible or using generic normal ranges for other parameters (see Appendix G). When the NCI-CTCAE is not applicable, laboratory values “out of normal ranges” will be summarized.

For each laboratory parameter, each assessment performed from the 2nd day of cycle N to the 1st day of cycle N+1 will be assigned to cycle N. The 1st day of any cycle will be the date of the 1st study treatment infusion for this cycle.

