2.4.5.4 Analyses of laboratory variables

Hematological and clinical biochemistry toxicities will be assessed from laboratory test parameters defined in [Section 2.1.4.4](#).

The frequency of patients in each grade of laboratory test during treatment will be summarized. For patients with multiple occurrences of the same laboratory variable during the treatment, the maximum grade (worst) per patient will be used.

The denominator used for percentage calculation is the number of patients with at least 1 evaluation of the laboratory test during the considered observation period.

The summary table will present the frequency of patients with any grade of abnormal laboratory tests and with Grade 3-4 abnormal laboratory tests.

For the non-NCI gradable parameters (monocytes, eosinophils, basophils, chloride, total protein, BUN, LDH, urea, direct bilirubin), frequency of evaluable patients outside normal ranges will be provided.

Regarding calculated creatinine clearance, a summary of the lowest value recorded by patient will be provided using summary statistics. Frequencies by class (≥ 90 mL/min, ≥ 60 mL/min and < 90 mL/min, ≥ 30 mL/min and < 60 mL/min, ≥ 15 mL/min and < 30 mL/min, < 15 mL/min) will also be provided.

Moreover, a listing of possible Hy's law cases identified (eg, patients with any elevated AST or ALT of > 3 ULN **and** elevated Total bilirubin > 2 ULN, 1 day apart), will be provided, displaying ALT, AST, Total bilirubin and ALP values.

A summary reporting the number of patients with at least one positive serum pregnancy test during the study will be provided.

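### The Cockcroft-Gault numerator in Protocol Appendix E and SAP 2.5.1 closes its bracket in the wrong place, so every adult gets a negative clearance (confirm on the original pages)

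*Protocol*

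**What the plan says.** Protocol Appendix E gives creatinine clearance as a fraction multiplied by a sex factor (1.00 for men, 0.85 for women). The numerator reads "140 - \text{age [years]} \times \text{body mass [kg", and its closing parenthesis comes only after the body-mass unit. The denominator is "Plasma creatinine (mg/dL)} \times 72". SAP 2.5.1 prints the same expression, attributes it to Cockcroft and Gault, and lists it among the formulas to be used for deriving parameters. Neither document gives another form of the equation.

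The formula is used in three places:

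- **Eligibility.** Exclusion E 18c removes patients with serum creatinine above 1.5 x ULN, "except if calculated creatinine clearance ≥ 60 mL/min (as per Cockcroft-Gault formula, see Appendix E" (synopsis; repeated in Protocol 7.2.2).
- **Dosing.** In Protocol 8.2.3.2, Table 3, clearance is calculated when creatinine exceeds 1.5 x ULN. At 50 mL/min or more the dose is unchanged, and from 30 to below 50 it drops one level. Below that the instruction is "If clearance <30 mL/min, withdraw from study treatment". Footnote b of the table points to Appendix E.
- **Safety analysis.** SAP 2.1.4.4 lists "creatinine clearance (calculated according to both Cockcroft-Gault formula, see" section 2.5.1. SAP 2.4.5.4 then states: "Regarding calculated creatinine clearance, a summary of the lowest value recorded by patient will be provided", with frequencies in classes cut at 15, 30, 60 and 90 mL/min.

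**The concern.** With a single bracket around the whole numerator, ordinary operator precedence multiplies age by weight first and then subtracts the product from 140. That product exceeds 140 for any adult, so the clearance comes out below zero. The documents show the fault without any outside source, because they compare this quantity with positive cut-offs that it could never reach.

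The appendix is the reference to which sites are sent for an eligibility exception and a withdrawal rule, and SAP 2.5.1 is the programmer's derivation. Taken at face value:

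- the E 18c exception would be empty;
- the first two Table 3 rows for raised creatinine would never apply;
- the SAP class table would put all patients with a calculated value in the lowest class. That summary is not restricted to patients with raised creatinine.

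**Working it through.** **Inputs from the documents.** The numerator, denominator and sex factors come from Protocol Appendix E and SAP 2.5.1. The minimum age is 18 (E 02, Protocol 7.2.1). The cut-offs are 60 mL/min (E 18c), 30 and 50 mL/min (Table 3), and 15/30/60/90 mL/min (SAP 2.4.5.4). The documents contain no worked clearance value to reproduce.

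**Formulas** (G is the sex factor, Cr is creatinine in mg/dL)

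- As printed: (140 - age × kg) / (72 × Cr) × G
- Bracket closed after age: (140 - age) × kg / (72 × Cr) × G

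**Sign.** 72 × Cr and G are positive, so the sign is that of the numerator. As printed, it is negative when kg > 140/age. At age 18 the limit is 140/18 = 7.8 kg, and it falls as age rises.

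**Range.** Over ages 18 to 85, weights 40 to 120 kg and creatinine 0.5 to 3.0 mg/dL, the highest printed value is at age 18, 40 kg, Cr 3.0, female: (140 - 720)/216 × 0.85 = -2.3 mL/min. Over a wider grid (ages 18 to 99, 30 to 150 kg, Cr 0.4 to 5, both sexes) the maximum is -0.9, at (140 - 540)/360 × 0.85. No value on either grid reaches zero.

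**Illustrations.** The patients below are assumed and not taken from the documents; all are women, so G = 0.85. A creatinine of 1.6 exceeds 1.5 x ULN if the ULN is below 1.6/1.5 = 1.07 mg/dL. A creatinine of 1.8 does so if the ULN is below 1.8/1.5 = 1.2 mg/dL.

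| Rule | Age, kg, Cr | As printed | Corrected | Consequence |
|---|---|---|---|---|
| E 18c | 40, 85, 1.6 | -24.1 | 62.7 | excluded vs eligible |
| Table 3 | 40, 70, 1.6 | -19.6 | 51.6 | withdraw vs no change |
| Table 3 | 55, 70, 1.8 | -24.3 | 39.0 | withdraw vs reduce one level |
| Table 3 | 75, 60, 1.8 | -28.6 | 25.6 | withdraw either way |
| SAP class | 55, 70, 0.8 | -54.7 | 87.8 | <15 vs 60 to <90 |
| SAP class | 80, 45, 4.0 | -10.2 | 8.0 | <15 either way |

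First row in full. As printed: (140 - 3400)/(72 × 1.6) × 0.85 = -3260/115.2 × 0.85 = -24.1. Corrected: (100 × 85)/115.2 × 0.85 = 62.7.

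Closing the bracket after age therefore gives positive values on the scale of the plan's own cut-offs.

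**The case against.** The strongest objection is provenance. The point rests on the position of one bracket in a typeset fraction, and it was read from text extracted from the PDFs. Extraction of these files is imperfect elsewhere: the column heads of SAP Table 19 are displaced compared with Table 4 in Protocol Appendix A. The match between the two documents is only partial corroboration. A formula copied from protocol to SAP would look identical whether the slip was genuine or one layout had been misread twice. This stands, and the text alone cannot settle it. Against it, other typeset fractions came through coherently, such as the tumor-shrinkage, antibody-incidence and dose-intensity formulas in the SAP.

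The second objection is practical. The equation is named wherever it is used, all its terms and constants are present, and a negative clearance would show at the first calculation. Sites and programmers would probably apply the familiar form. Clearance matters for eligibility and dosing only when creatinine exceeds 1.5 x ULN, and the SAP use is one descriptive safety summary. This also stands. It limits the severity, but it does not make the printed expression usable.

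**Conclusion.** The concern holds, as a minor one. In the text available, both documents define a clearance that is negative for every adult, and their own thresholds cannot be applied to it. The table of illustrations shows what a literal reading would do. It is not a forecast of misclassified patients, because that would require someone to accept and act on negative clearances.

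The objective response rate, the test requiring 7 responses in 29 patients, the interim boundaries and the Bayesian safety rule do not use this quantity. The conclusion assumes that the bracket sits in the same place on the original pages. If those pages close it after age, the point falls away.

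**What to change.** Check the original pages of Protocol Appendix E and SAP 2.5.1. If they show the same bracket, replace the expression in both documents with:

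(140 - age [years]) × body mass [kg] / (plasma creatinine [mg/dL] × 72) × sex factor (male 1.00, female 0.85)

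The cut-offs in E 18c, Table 3 and SAP 2.4.5.4 stay as they are. The cost is one bracket in each document; no sample size, threshold or analysis changes.
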